Research question and objectives	
Research question: The research question is whether the risk minimisation measures (DHPC and updated SmPC) were effective in:
 
 • Increasing the knowledge of physicians/HCPs about the updated safety information when prescribing TMZ • Influencing the prescribing behaviour of physicians for TMZ in indications no longer approved by the Competent Authorities 
Primary objective:
 
 • to evaluate the proportion of targeted physicians who received, understood and agreed to implement the updated information about TMZ provided in the DHPC 
Secondary objectives:
 
 • to evaluate the proportions of prescriptions within the licensed indication after the update of the SmPC • to evaluate characteristics of prescribing conditions in terms of patient characteristics (age, gender) and prescription information (form of administration, dosage, new or repeat prescription, planned duration of usage, treatment situation, reason for choosing TMZ, discontinuation plan for patients already on TMZ).

Countries of study	Bulgaria, Czech Republic, Estonia, France, Hungary, Latvia, Lithuania, Poland, Portugal, Romania, Slovakia, and Spain
Author	IMS Health RWES [name], PhD, Engagement Manager, RWES/HEOR [name]; email: [contact] [name], Medical Director, RWES/HEOR, IMS Health, [name]. Email: [contact]
MAH(s)	Consortium of companies represented by Lupin (Europe) Limited. Please refer to Annex 3; List of Companies (and/or their Affiliates and licensors) that are part of the consortium
MAH contact person	Joint PASS MAH contact person: [name], Head of Pharmacovigilance / EU Qualified Person for Pharmacovigilance (EU QPPV), Lupin (Europe) Limited, located at: Hormosan Pharma GmbH [name] E-Mail: [contact] [contact]

IMS is a partner centre of the ENCePP scientific network which is coordinated by the European Medicines Agency. IMS is dedicated to excellence in research by adhering to the ENCePP Guide on Methodological Standards and promoting scientific independence and transparency.

2. LIST OF ABBREVIATIONS AND DEFINITIONS OF TERMS

Abbreviation	Definition
AE	Adverse event
AR	Adverse reaction
ASOCS	Association of Opinion and Behaviour in health field research companies
CHMP	Committee for Medicinal Products for Human Use
CI	Confidence interval
DHPC	Direct healthcare professional communication
EMA	European Medicines Agency
ENT	Ear/Nose/Throat
EphMRA	European Pharmaceutical Marketing Research Association
GVP	Good pharmacovigilance practices
GP	General practitioner
HCP	Health care professional
IR	Immediate release
MAH	Marketing authorization holder
MR	Modified release
PASS	Post-authorization safety study
PIL	Patient information leaflet
PRAC	Pharmacovigilance Risk Assessment Committee
PSUR	Periodic safety update report
RMM	Risk minimization measures
RMP	Risk minimization plan
SAE	Serious adverse event
SAP	Statistical analysis plan
SAR	Serious adverse reaction
SOP	Standard operating procedures
SmPC	Summary of product characteristics
STROBE	Strengthening the reporting of observational studies in epidemiology
TMZ	Trimetazidine

4.2 Rationale and background

TMZ-containing medicinal products were indicated in EU for various cardiology, ophthalmology and otolaryngology indications.

Otolaryngology and ophthalmology indications included:

- i. Ancillary symptomatic treatment of vertigo and tinnitus and
- ii. Ancillary treatment of visual acuity decrease and visual field disturbances due to vascular reasons

On 22 April 2011, France had requested the Committee for Medicinal Products for Human Use (CHMP) to give its opinion under Article 31 of Directive 2001/83/EC on whether the marketing authorisation for TMZ-containing medicinal products will be maintained, varied, suspended or withdrawn.

The review conducted by the CHMP concluded that the evidence of the efficacy and safety in the ophthalmology and otolaryngology indications, initially suggested by the studies on the basis of multiple assessments was considered weak due to the methodology applied to the investigation and was no longer recommended since September 2012 (3).

Potential prescribers were informed of this change in the indication of TMZ through "Direct Healthcare Professional Communications" (DHPCs) and other appropriate notifications.

The survey presented here is designed to evaluate the effectiveness of these risk minimization measures (RMM). Knowledge, attitude and behaviour of the physicians in the targeted countries about the content of the DHPC and the updated SMPC are evaluated. Furthermore, the proportion of prescriptions within the licensed indication and the prescribing conditions will be analyzed. In a parallel protocol, a drug utilization study will be conducted in which the effect of the restriction on the use of TMZ will be assessed.

4.3 Research question and objectives

Research question:

The research question is whether the risk minimisation measures (DHPC and updated SmPC) were effective in:

- Increasing the knowledge of physicians/HCPs about the updated safety information when prescribing TMZ
- Influencing the prescribing behaviour of physicians for TMZ in indications no longer approved by the Competent Authorities

Primary objective:

- to evaluate the proportion of targeted physicians who received, understood and agreed to implement the updated information about TMZ provided in the DHPC

Secondary objectives:

LUP/TMZ/2014/001a

- to evaluate the proportions of prescriptions within the licensed indication after the update of the SmPC
- to evaluate prescribing conditions in terms of patient characteristics (age, gender) and prescription information (form of administration, dosage, new or repeat prescription, planned duration of usage, treatment situation, reason for choosing TMZ, discontinuation plan for patients already on TMZ).

4.4 Study design

This is a multinational, cross-sectional, non-interventional and anonymous survey carried out among physicians. It will be conducted through a web-questionnaire among prescribers and potential prescribers of TMZ in the 12 countries where TMZ is being commercialized (Bulgaria, Czech Republic, Estonia, France, Hungary, Latvia, Lithuania, Poland, Portugal, Romania, Slovakia, and Spain).

4.5 Population

Inclusion criteria:

- Physicians prescribers, or potential prescribers, of TMZ
 - ENT-specialists,
 - ophthalmologists
 - cardiologists
 - others (GPs, internists, geriatricians)

Exclusion criteria:

- Physicians who do not treat patients or who may have a conflict of interest (i.e. physicians employed by regulatory bodies or pharmaceutical industries),
- Physicians who do not know TMZ

4.6 Variables

The collected information includes:

- Physician related data:
 - Knowledge of the physicians about the licensed use of TMZ
 - demographics
 - type of practice
 - awareness and knowledge of the safety information about TMZ presented in the updated SmPC and the DHPC
 - source of knowledge
 - physician's intention to consider the safety warnings
- Drug utilization data:
 - age, gender of patient
 - indication for which TMZ was prescribed
 - form of administration (immediate/ modified release tablet, oral solution) and dosage
 - new or repeat prescription
 - planned duration of usage
 - treatment situation (add-on, switch, reason for switch, first line therapy, other)
 - reason for choosing TMZ
 - discontinuation plan for patients already on TMZ

4.7 Data sources

The survey will collect data from the following data sources:

- Physicians files (IMS Medical Radar files) for gender, specialty and region,

LUP/TMZ/2014/001a

- Data collected through a web questionnaire, including
 - aggregated prescription data
 - general questions about prescription habits of the participating physicians

4.8 Study size

The sample size calculation is based on the survey objective, *i.e.* to evaluate the prescribers and potential prescriber awareness of the updated safety information about TMZ in the DHPC and the updated SmPC.

For a confidence interval of 95% and a precision of 2.7%, a total of 1320 analyzable web-questionnaires will be needed for the overall sample in the twelve countries participating in the survey.

4.9 Data analysis

All analysis will be descriptive in nature and no statistical comparison will be done in this study. Results will be presented overall, by country and per specialty.

Quantitative data will be summarized descriptively using *n*, mean, median, standard deviation, minimum and maximum. Categorical data will be summarized using frequency and percentage. 95% confidence interval (Wald's) may be constructed around the percentage values for some variables. Some of the variables may also be summarized by country.

The proportion of targeted physicians who received, understood and agreed to implement the updated information about TMZ provided in the DHPC will be calculated.

All variables will be analyzed in total and separately for ophthalmologists, ENT specialists, cardiologists and others based on the information provided.

In a first step, calculations will be performed on raw data.

In a second step, the results will be weighted according to the real proportion of physicians in each country in order to accurately reflect the population that the survey seeks to measure.

For each country, the results will be reported according to the prescribers' specialty distributed proportionally to their weight within the IMS Medical Radar reference lists.

Possible selection bias will be assessed by comparing the distributions of available characteristics (e.g. region, age, gender, type of practice and specialty) between respondent and non-respondent physicians.

4.10 Milestones

- Start of data collection - Fieldwork: 20 November 2014
- End of data collection - Fieldwork: 20 December 2014
- Final report of study results: 31 March 2015.

5. AMENDMENTS AND UPDATES:

A previous version was submitted entitled "A cross-sectional, multi-national survey to investigate the unlicensed use of Trimetazidine (TMZ) for various Ophthalmology and Otolaryngology indications." 05 September 2013 (Draft_1.0)

The current protocol is a thoroughly revised version based on PRAC comments.

6. MILESTONES

- Start of data collection: 20 November 2014
- End of data collection: 20 December 2014
- Final report of study results: 31 March 2015.

7. RATIONALE AND BACKGROUND

Three pharmaceutical forms of TMZ- containing medicinal products are available in EU: 20 mg tablet, 20 mg/ml oral solution and 35 mg modified release (MR) tablet.

TMZ-containing medicinal products were indicated in EU for various cardiology, ophthalmology and otolaryngology indications.

Otolaryngology and ophthalmology indications included:

- Ancillary symptomatic treatment of vertigo and tinnitus and
- Ancillary treatment of visual acuity decrease and visual field disturbances due to vascular reasons

The indication in otology was authorized in 12 European Union Member States. The recommended dosage of TMZ 20 mg was one tablet three times a day, i.e. a daily dose of 60 mg. The equivalent dosage of TMZ 35 mg is one tablet in the morning and one tablet in the evening at mealtimes, i.e. a daily dose of 70 mg.

TMZ was indicated in ophthalmology in 7 countries in the European Union. In all countries, the recommended dosage of TMZ 20 mg is one tablet three times daily, i.e. a daily dose of 60 mg and the equivalent dosage of TMZ 35 mg is one tablet morning and evening, i.e. a daily dose of 70 mg (1).

Medicines containing TMZ are being marketed in Bulgaria, Cyprus, Czech Republic, Denmark, Estonia, France, Germany, Greece, Hungary, Ireland, Italy, Latvia, Lithuania, Luxembourg, Malta, Poland, Portugal, Romania, Slovakia, Slovenia and Spain (2)

On 22 April 2011, France had requested the Committee for Medicinal Products for Human Use (CHMP) to give its opinion under Article 31 of Directive 2001/83/EC on whether the marketing authorisation for TMZ-containing medicinal products will be maintained, varied, suspended or withdrawn.

The review conducted by the CHMP concluded that the evidence of the efficacy and safety in the ophthalmology and otolaryngology indications, initially suggested by the studies on the basis of multiple assessments was considered weak due to the methodology applied to the investigation and was no longer recommended since September 2012 (3).

Potential prescribers were informed of this change in the indication of TMZ through “Direct Healthcare Professional Communications” (DHPCs) and other appropriate notifications. A drug utilization study to monitor the compliance of prescribers regarding the restricted use of TMZ in ophthalmology and otolaryngology indications has been requested by the CHMP.

The analysis of the database generated from the current study will help in planning and executing appropriate risk minimization measures to be taken. The survey presented here is designed to evaluate the knowledge, attitude and behaviour of the physicians in the targeted countries about the content of the DHPC and the updated SMPC. In a parallel protocol, a drug utilization study will be conducted in which the effect of the restriction on the use of TMZ will be assessed.

7.1 RATIONALE FOR COUNTRY SELECTION

The selection of the countries to be involved in the survey was done in order to meet all the following criteria:

- European countries in which TMZ is currently registered and marketed: Bulgaria, Czech Republic, Estonia, France, Hungary, Latvia, Lithuania, Poland, Portugal, Romania, Slovakia, and Spain and
- European countries in which the physicians were targeted for the DHPC.

The survey will be conducted in the twelve following countries: Bulgaria, Czech Republic, Estonia, France, Hungary, Latvia, Lithuania, Poland, Portugal, Romania, Slovakia, and Spain.

7.2 RATIONALE FOR THE SELECTION OF THE SPECIALTIES

The MAHs are required to conduct a study to monitor the effectiveness of the DHPC in order to strengthen risk minimization measures for TMZ.

The survey will be conducted among the following specialists who were targeted for the DHPC:

- ENT-specialists,
- ophthalmologists
- cardiologists
- others (GPs, internists, geriatricians)

8. RESEARCH QUESTION AND OBJECTIVES

8.1 RESEARCH QUESTION

Research question:

The research question is whether the risk minimisation measures (DHPC and updated SmPC) were effective in:

- Increasing the knowledge of physicians/HCPs about the updated safety information when prescribing TMZ
- Influencing the prescribing behaviour of physicians for TMZ in indications no longer approved by the Competent Authorities

8.2 OBJECTIVE

Primary objective:

- to evaluate the proportion of targeted physicians who received, understood and agreed to implement the updated information about TMZ provided in the DHPC

Secondary objectives:

- to evaluate the proportions of prescriptions within the licensed indication after the update of the SmPC
- to evaluate characteristics of prescribing conditions in terms of patient characteristics (age, gender) and prescription information (form of administration, dosage, new or repeat prescription, planned duration of usage, treatment situation, reason for choosing TMZ, discontinuation plan for patients already on TMZ).

9. RESEARCH METHODS

9.1 STUDY DESIGN

This is a multi-national, cross-sectional, non-interventional and anonymous web-based survey carried out among physicians.

9.2 SETTING

The survey will be conducted among prescribers, or potential prescribers, of TMZ in the selected countries (Bulgaria, Czech Republic, Estonia, France, Hungary, Latvia, Lithuania, Poland, Portugal, Romania, Slovakia, and Spain).

[figure not shown]

Figure 1: Study scheme and main timelines

9.2.1 Inclusion criteria

The survey will be conducted among physicians meeting the following inclusion criteria:

- Prescribers, or potential prescribers, of TMZ, i.e. physicians who know the drug,
- Specialists of any of those targeted for the DHPC:
 - ENT-specialists,
 - ophthalmologists
 - cardiologists
 - others (GPs, internists, geriatricians)

9.2.2 Exclusion criteria

Inactive and retired physicians (when documented information is available to identify them) will be deleted from the contact lists before randomisation.

The following exclusion criteria will be checked at the beginning of the web-questionnaire:

- Physicians who do not treat patients or who may have a conflict of interest (i.e. physicians employed by regulatory bodies or pharmaceutical industries),
- Physicians who do not know TMZ

9.3 VARIABLES

In this study, both physician related data about their knowledge and prescribing attitude for TMZ and drug utilization data will be collected.

Physician related data include:

- demographics
- type of practice
- knowledge of the physicians about the licensed use of TMZ
 - awareness and knowledge of the safety information about TMZ presented in the DHPC and in the updated SmPC
 - sources of knowledge
- physician's intention to consider the safety warnings

The following drug utilization data will be collected:

- age, gender of patient
- indication for which TMZ was prescribed
- form of administration (immediate/ modified release tablet, oral solution) and dosage
- new or repeat prescription
- planned duration of usage
- treatment situation (add-on, switch, reason for switch, first line therapy, other)
- reason for choosing TMZ
- discontinuation plan for patients already on TMZ

9.4 DATA SOURCES

The survey will collect data from the following sources:

- physicians files (IMS Medical Radar files)
- information collected by a web questionnaire, including
 - aggregated patient data
 - general questions about prescription habits of the participating physicians

The questionnaire will be designed by experienced persons and will include both open and close ended questions. The web questionnaire completion is estimated to take 10 to 15 minutes for the general part and an additional 5 minutes per patient for the drug utilization data. Before being finalized, the questionnaire will be administered to/ tested by 6-8 physicians in order to make sure it is well understood and the wording appropriate to the survey topic. Physicians' comments will be implemented in the final version. Moreover, the questionnaire will be translated using the back and forth method (translation from English to local language, then again to English) to make sure the appropriate wording is used.

9.5 STUDY SIZE

9.5.1 Sampling plan

The statistical unit is the physician. For each selected country, the sample survey will combine physicians recruited from two data sources:

- IMS Medical Radar's reference lists of required specialists.

For the drug utilization data, the statistical unit is the prescription.

These lists will be restricted to the targeted specialists' population, i.e. selected specialists who are currently active and not retired in 2014 at the time of the survey.

As per sample size defined below and the number of selected countries and specialties, physicians will be stratified only by country and specialty. Thereby some specialties will be combined, resulting in 4 groups of physicians:

- ENTs
- ophthalmologists
- cardiologists
- others (GPs, internists, geriatricians).

Other criteria such as region, age and gender of the prescriber are less relevant than country and specialty, since they may not be available in all countries or not be a determinant as important as country or specialty.

A random stratified sampling method will be applied. As a first step, all lists will be merged, and then the eligible physicians will be divided into homogeneous groups, called strata, which are mutually

exclusive (a physician can only belong to one stratum). This stratification will be done based on the following criteria:

- Country: 12 possibilities,
- Specialty: 4 possibilities.

Physicians are not evenly distributed across these specialties. Specialties/ groups could be combined if needed. Thus, up to $12 \times 4 = 48$ strata will be formed.

Table 1: Strata definition

Stratum ID	Country	Specialty
1	Bulgaria	ENT-specialists,
2		ophthalmologists
3		cardiologists
4		GPs, internists, geriatricians
5	Czech Republic	ENT-specialists,
6		ophthalmologists
7		cardiologists
8		GPs, internists, geriatricians
9	Estonia	ENT-specialists,
10		ophthalmologists
11		cardiologists
12		GPs, internists, geriatricians
13	Country 4-12	repeat as above

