Based on IMS Medical Radar experience from previous similar surveys and estimates, about 10-15% of physicians will not complete the questionnaire because they do not know TMZ (the questions on prescribing conditions would not be applicable to them) or because they have to interrupt the interview due to an emergency (rare). Taking this into account, recruitment of physicians should continue until 1320 analyzable questionnaires have been reached.

Table 2: Number of analyzable physician interviews required per country

Country	Sample size objective
Bulgaria	100
Czech Republic	80
Estonia	80
France	160
Hungary	100
Latvia	80

Lithuania	100
Poland	120
Portugal	150
Romania	100
Slovakia	100
Spain	150
Total Sample Size	1320

Sample adjustment:

Since the relative weight of each country and of each specialty in the sampling plan is different from its real relative weight in the target lists, the extrapolation of the raw survey results to the overall target population would not be relevant.

A sample adjustment will be performed. The survey results will be weighted to reflect the real proportion of the two countries and within each country to reflect the real proportion of each specialty in order to extend the survey results to the overall target population. Both unweighted (i.e. raw data) and weighted results will be presented in the report.

A weight variable will be applied to each statistical unit (i.e. the analyzable physician) during the results calculation in order to correct any over-or under-sampling that may have occurred for a country or specialty. This weight variable will indicate how many unit(s) of the population of interest an observation will count in a statistical procedure. Its value will change per country and per specialty. The weights will be normalized to obtain their sum equal to the sample size.

In order to fill-in each stratum of the sample survey from the external list and the IMS Medical Radar file, an independent sample will be selected per stratum through a simple random sampling without replacement.

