Quantitative data will be summarized descriptively using n, mean, median, standard deviation, minimum and maximum. Categorical data will be summarized using frequency and percentage. 95% confidence interval (Wald's) may be constructed around the percentage values for some variables. Some of the variables may also be summarized by country.

Analysis for primary objective:

The proportion of targeted physicians who received, understood and agreed to implement the updated information about TMZ provided in the DHPC will be calculated. Analysis will be done in total and separately by specialty (ophthalmologists, ENT-specialists, cardiologists and others) using proportions and the corresponding 95% Wald confidence intervals).

Analysis for the secondary objectives:

The following variables will be analyzed separately for ophthalmologists, ENT specialists, cardiologists and others based on the information provided:

- proportion of prescriptions with the licensed indication will be summarized
- characteristics (age, gender) of patients to whom TMZ is prescribed will be summarized categorically.
- Data on type of TMZ prescribed (IR/MR/Oral Solution) will be summarized through frequencies and percentages.
- Proportion of cases where TMZ was prescribed as a combination / add-on treatment will be summarized through frequencies and percentages.
- Reasons for prescribing TMZ over other drugs will be summarized categorically.
- Timeframe to keep patient on TMZ will be summarized categorically.
- Discontinuation plan for the patients already on TMZ will be listed.

In a first step, calculations will be performed on raw data. No projection factor will be applied to generalize the results to the entire prescribers' universe. As a consequence, the line "Overall – unweighted results" will show only the results observed on the overall sample, and will not reflect the

countries' universe since this sample is not proportional to the size of the external list of physicians or IMS Medical Radar reference files in each country.

In a second step, the results will be weighted according to the real proportion of physicians in each country in order to accurately reflect the population that the survey seeks to measure.

For each country, the results will be reported according to the prescribers' specialty distributed proportionally to their weight within the IMS Medical Radar reference lists.

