10.2.1 Physicians compensations

Physicians will be offered a compensation for the time spent participating in this survey (which they may refuse). The time to complete the survey is estimated to be between 10 to 15 minutes, plus an additional 5 minutes for each prescription questionnaire..

The amount of this compensation will be determined according to the EphMRA recommendations and the Association of Opinion and Behaviour in health field research companies (ASOCS) charter, and which states:

“When it is necessary to compensate a physician in return to the time spent during an interview or a group meeting, the compensation must not exceed the fees commonly taken by the physician for his/her advice or consultation and must be proportional to the time provided. The compensations should be clearly stated prior to the physician's participation in the survey. They must be declared to the tax authorities in accordance with applicable laws”.

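### Prescription results have no clustered variance and no defined prescription weight, although physicians are sampled and may each report several prescriptions

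*Protocol*

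**What the plan says.** Section 9.5.1 gives two units. For the survey, "The statistical unit is the physician"; a few lines later, "For the drug utilization data, the statistical unit is the prescription". Only physicians are drawn, by simple random sampling within up to 48 country-by-specialty strata.

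Several prescriptions per physician are foreseen but not counted. Section 9.4 allows "an additional 5 minutes per patient for the drug utilization data", and section 10.2.1 bases compensation on 10 to 15 minutes "plus an additional 5 minutes for each prescription questionnaire". No number, cap or selection rule is given.

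The first secondary objective (section 8.2) is "to evaluate the proportions of prescriptions within the licensed indication after the update of the SmPC".

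On intervals, section 9.7.1 specifies 95% Wald intervals for the primary objective and makes them optional for some other variables. Its secondary-objective bullets speak only of summaries and listings. Section 9.7.3 then says, without restriction, that 95% intervals will be calculated for variables. Correlation within physician is not mentioned.

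On weights, section 9.5.2 states "A weight variable will be applied to each statistical unit (i.e. the analyzable physician) during the results calculation" and "The weights will be normalized to obtain their sum equal to the sample size". Section 9.7.1, directly after the list of secondary analyses, says that "the results will be weighted according to the real proportion of physicians in each country". Prescription volume does not appear in the variable list of section 9.3.

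**The concern.** Forms from one doctor share that doctor's specialty, habits and knowledge of the restriction, so they carry less information than the same number of forms from different doctors. A Wald interval with the number of prescriptions as its denominator ignores this.

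The weighting does not fit the unit. Section 9.5.2 identifies the statistical unit with the physician when it defines the weight, while section 9.5.1 has made the prescription the unit for these data. A count of physicians per stratum says nothing about how much trimetazidine each of them prescribes.

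At stake is the second half of the research question in section 8.1, the influence on prescribing behaviour. The reported on-label proportion could carry an interval that overstates its certainty. Its weighted value could also describe the average physician when the objective asks about prescriptions.

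**Working it through.** **The plan's own figure.** With P = 0.50, e = 0.027 and z = 1.96 (section 9.5.2), n = P(1 − P)z²/e² = 0.25 × 3.8416 / 0.000729 = 1317.4. The protocol states 1316, which agrees for practical purposes. At the planned 1320 physicians the half-width is 1.96 × √(0.25/1320) = 2.70 points. This is a physician-level figure. No sample size or precision is stated for prescriptions.

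**Clustering.** Inputs: 1320 physicians (section 9.5.2, Table 2) and P = 0.50 (same section). The number of forms per physician, m, and the ICC are not in the protocol. I assume m = 2, 3, 5 and ICC = 0.1, 0.3, 0.5, with equal m, every physician contributing and no further loss from unequal weights.

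- Design effect: DEFF = 1 + (m − 1) × ICC
- Naive half-width: 1.96 × √(0.25/(1320m))
- Clustered half-width: naive × √DEFF
- True coverage of the naive interval: 2Φ(1.96/√DEFF) − 1

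| m | Naive half-width (points) | Clustered half-width, ICC 0.1 / 0.3 / 0.5 | Coverage of naive interval, ICC 0.1 / 0.3 / 0.5 |
|---|---|---|---|
| 1 | 2.70 | 2.70 / 2.70 / 2.70 | 95.0% / 95.0% / 95.0% |
| 2 | 1.91 | 2.00 / 2.17 / 2.34 | 93.8% / 91.4% / 89.0% |
| 3 | 1.56 | 1.71 / 1.97 / 2.20 | 92.6% / 87.9% / 83.4% |
| 5 | 1.21 | 1.43 / 1.79 / 2.09 | 90.2% / 81.4% / 74.2% |

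For m above 1 the correct half-width is √1.1 = 1.05 to √3.0 = 1.73 times the naive one. In a cell of 40 physicians, the protocol's own threshold for analysis, m = 3 and ICC = 0.3 move the half-width from 8.95 to 11.32 points.

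**Weighting.** All figures here are assumed. Suppose 20% of physicians write five times as many prescriptions as the others and are 90% on-label, the other 80% are 60% on-label, and each physician returns the same number of forms.

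- Physician-weighted result: 0.2 × 0.9 + 0.8 × 0.6 = 66.0%
- Proportion of prescriptions: (0.2 × 5 × 0.9 + 0.8 × 0.6) / (0.2 × 5 + 0.8) = 1.38/1.80 = 76.7%

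With equal volumes both are 66.0%. They also agree if on-label use is the same in both groups. If instead each physician reported every prescription in a common time window, forms would follow volume, and giving each form its physician's stratum weight would estimate the proportion of prescriptions correctly. The result therefore depends on a selection rule that the protocol does not give.

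**The case against.** The strongest defence is that much of this is silence. The protocol nowhere says that prescriptions are independent; that follows only from the choice of unit together with the Wald interval. Section 9.7.1 plans no interval by name for the secondary objectives, and a clustered variance is commonly left to a statistical analysis plan, which is not shown. This lowers confidence. It does not remove the point, because section 9.7.3 calls for intervals on variables generally and the unit and the type of interval are set in the protocol.

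A second defence is that overall precision stays adequate. Every clustered half-width in the table is within 2.70 points. That holds if all 1320 physicians contribute; section 9.2.1 also admits potential prescribers, who may have no prescription to report. In any case the coverage shortfall does not depend on how many physicians contribute.

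Third, the questionnaire is a stand-alone document not seen here, and its general questions on prescribing habits (section 9.4) may already record volume. Sections 9.8.2 and 10.4 provide for keeping the database. Both points make the fix cheaper.

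Fourth, analysis by specialty should limit the mixing of cardiologists with ENT and eye specialists, and a parallel drug utilization study examines the effect of the restriction. This lowers the severity. Section 4.9 still calls for results in total.

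A reader might infer that the protocol gives each prescription the physician's weight, or that the result is biased toward low-volume prescribers. The text supports neither: it leaves prescriptions without a defined weight, and the bias needs form numbers that do not follow volume and a link between volume and on-label use.

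**Conclusion.** The point holds in a conditional form. If physicians report more than one prescription and the ICC is above zero, a Wald interval on prescriptions is too narrow. Over assumed values of m from 2 to 5 and ICC from 0.1 to 0.5, coverage of a nominal 95% interval is about 94% down to 74%. At m = 1 this part disappears.

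Separately, the weight is defined for a different unit from the one being analysed. Where physicians give similar numbers of forms whatever their volume, and volume is related to on-label use, the weighted figure does not estimate the quantity in the secondary objective. The gap of 66.0% against 76.7% illustrates this and is not a prediction. It can arise at m = 1 too.

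It would go too far to say that the result is no proportion of prescriptions at all: the unweighted figure, which will also be reported, is a proportion of the prescriptions sampled. The primary objective uses the physician as its unit and is unaffected. Because the objective concerned is secondary and descriptive, this is a matter that should be fixed, held with moderate confidence.

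**What to change.** - Compute every prescription-level interval with physician as cluster within country-by-specialty strata, for example by Taylor linearization.
- State in the protocol how many prescriptions each physician reports and how they are chosen. This must be settled before fieldwork, since it cannot be recovered afterwards.
- Then either weight each form by physician weight × reported trimetazidine volume in a fixed period ÷ forms completed, or keep the physician weight and label the weighted result a physician-weighted mean.
- Reconcile the two definitions of the statistical unit in sections 9.5.1 and 9.5.2, and confirm that the analysis file holds individual forms with a coded physician identifier. Sections 9.4 and 10 describe the data as aggregated, which sits badly with a prescription-level analysis.

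The cost is one short volume question if the questionnaire lacks it, a cluster specification in the analysis program, a second weight if that option is taken, and wider secondary intervals. The physician sample size does not change.
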